## **12.2 Statistical Analysis**

The primary objective of this double-blind, placebo controlled randomized trial is to compare the participant-reported pain scores taken on an 11-point numerical rating scale (NRS-11) between subjects who received Gabapentin and controls who received placebo on day-7 post-scrotal surgery. The secondary objective is to determine whether the addition of gabapentin for post-operative pain control reduces narcotic intake. This study will also explore the effect gabapentin has on symptom modification.

Assuming a baseline NRS-11 score of 3.8 (from previous study) and a goal is to detect a two-point difference (reduction) in the day-7 pain score between the two groups, a sample size of 86 participants (43 per arm) will yield a power of 80% when using a two-sample t-test with a 0.05 two-

sided significance level. To account for potential loss to follow up and drop-out at a rate of 25%, each arm will require 43 study participants for a total recruitment of 86 study participants. This calculation assumes a standard deviation of 2.9, which is based on a previous study that looked at the effect of celecoxib in the same patient setting.

Approximately 150 to 250 microTESE procedures are conducted at our site annually. As a result, we plan to accrue and complete the study in 29 months (i.e. ~9 study participants per month).

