Descriptive statistics will be calculated to describe the cohort of study participants using N (%) and mean, median, range for categorical and continuous factors, respectively. A two-sample t-test or nonparametric Wilcoxon rank-sum test will be used, as appropriate, to compare the mean (median) participant-reported pain scores on day 7 post-scrotal surgery between the two arms. A chi-square test or Fisher's exact test will be used, as appropriate, to compare the proportion of narcotic use post-scrotal surgery between the two arms and to compare the proportion of adverse events experienced post-scrotal surgery between the two arms. Similar analyses will also be completed on the NRS-11 pain score, narcotic use, and reported adverse events on day-1 post-scrotal surgery. Generalized estimating equations (GEE) modeling will also be performed to compare NRS pain scores, assessed over all post-operative days 1 to 7, between the gabapentin and placebo groups. GEE allows for multiple observations per participant (i.e., pain scores for day 1 to day 7, per participant) and also allows for the incorporation of missing pain scores at some of the defined time points.

All p-values will be two-sided with statistical significance evaluated at the 0.05 alpha level. Ninety-five percent confidence intervals for all parameters of interest will be calculated to assess the precision of the obtained estimates. All analyses will be performed in R Version 3.6.1 (R Foundation for Statistical Computing, Vienna, Austria). Note: The statistical considerations section was written in conjunction with [name], MS, in the Division of Biostatistics and Epidemiology, Department of Healthcare Policy & Research.

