## 15. Data and Safety Monitoring Plan (DSMP)

- Adverse events will be recorded by the study nurse and clinical fellow during follow-up phone calls and clinic visits with each post-operative patient. Minor adverse events will be examined and reviewed for intervals of every 10 subjects during accrual. Any significant adverse events or grade 4 events possibly related to the study product will trigger a temporary cessation of the trial and full review by the principal investigator, as well as the WCM DSMB as to whether the study should continue.
- The WCM DSMB will be utilized in our investigator-initiated study, with evaluation of adverse events at specific intervals. This will occur at 6 month time periods.
- Data
  - Adverse event data
    - Major: Allergic reaction, suicidal behavior and ideation, driving impairment
    - Minor: dizziness, somnolence, peripheral edema, ataxia, fatigue, nystagmus, GI symptoms
  - Study-related data
    - Pain scores (NRS-11), Narcotic tablet tally, overall pain control satisfaction (Yes/No question)
  - Demographics

- Age, male infertility diagnoses (i.e. presence of varicocele), prior surgical history, current medications, historical lab evaluation (FSH, LH, total testosterone, semen analyses, sperm DNA integrity tests such as tunel or SCSA assay, karyotype data, y-microdeletion status), pathology results of testis biopsy
- Data safety
  - Data will be kept in REDCap, which is licensed by WCMC and is HIPAA compliant. Only study personnel will have access to the database. Hard or software copies of the database will not be allowed. The database will only be accessed within the WCMC network utilizing WCMC tagged devices. Subject identifiers will be replaced by study identifiers as soon as data collection is complete.

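### The day-7 pain comparison needs one pre-specified, covariate-adjusted mean difference: the plan leaves the effect measure open and makes no use of baseline factors it already collects

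*Combined protocol and SAP*

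**What the plan says.** Three parts of the document bear on this.

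- **Sizing (12.2).** The stated aim is that "a goal is to detect a two-point difference (reduction) in the day-7 pain score between the two groups", and the sample size "will yield a power of 80% when using a two-sample t-test" at a two-sided 0.05 level. The reference mean is 3.8. On spread: "This calculation assumes a standard deviation of 2.9".
- **Analysis (12.2).** For day 7: "A two-sample t-test or nonparametric Wilcoxon rank-sum test will be used, as appropriate, to compare the mean (median) participant-reported pain scores". No rule decides between the tests, neither is the default, and nothing says which result stands if they differ. A GEE model over days 1 to 7 is added, also with no covariates named. Confidence intervals of 95% are promised for all parameters of interest, but the parameter for day 7 is not fixed.
- **Baseline data.** Table 1 (6.1) schedules demographics and medical history before the study. Section 15 lists among the data to be held: "Age, male infertility diagnoses (i.e. presence of varicocele), prior surgical history, current medications, historical lab evaluation". None of these enters a pain comparison. Section 7.11 describes 1:1 permuted blocks and names no stratification factor.

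**The concern.** The trial is sized to answer a question about a mean, but the analysis may answer a different one. A Wilcoxon test does not estimate a two-point mean difference, and in general it is not a test of medians either. If the report gives a median difference, it cannot be set against the stated goal. Because the choice is unwritten, it will in practice be made with the scores in hand.

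The plan also collects baseline factors that could narrow the confidence interval and does not use them. If the 25% loss the plan allows for occurs, the trial falls a little short of 80% power, so even a modest gain in precision is worth having.

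**Working it through.** **Inputs.** From 12.2: difference 2, SD 2.9, reference mean 3.8 (so 1.8 under gabapentin), two-sided alpha 0.05, 43 per arm, 25% loss. Not in the documents: the share of within-arm variance in day-7 pain explained by age and prior surgery (R²). I assume 0.02 to 0.20.

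**1. The plan's sample size.** Normal approximation: n per arm = 2 × (1.960 + 0.842)² × 2.9² / 2² = 33.0, rounded up to 34. The exact t calculation also gives 34 (power 80.0%). Then 34 × 1.25 = 42.5, rounded up to 43, which is the plan's figure.

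**2. Unadjusted power after the planned loss.** 43 × 0.75 = 32.25, so 32 per arm. Noncentrality = 2 / (2.9 × √(2/32)) = 2 / 0.725 = 2.759. With 62 degrees of freedom, power is 77.5%. How the dropout allowance was applied is a separate sizing question; 32 is only the starting point here.

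**3. Power with two covariates.** Residual SD = 2.9 × √(1 − R²); degrees of freedom = 64 − 4 = 60.

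| Assumed R² | Residual SD | Noncentrality | Power, 32 per arm |
|---|---|---|---|
| 0 | 2.900 | 2.759 | 77.47% |
| 0.02 | 2.871 | 2.787 | 78.3% |
| 0.05 | 2.827 | 2.830 | 79.5% |
| 0.10 | 2.751 | 2.908 | 81.6% |
| 0.20 | 2.594 | 3.084 | 85.9% |

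If the covariates explain nothing, the cost is under 0.1 percentage point (77.5% to 77.47%). At 34 analysed per arm, the unadjusted 80.0% becomes 81.9%, 83.9% and 87.9% for R² of 0.05, 0.10 and 0.20.

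**4. Does the choice of effect measure matter?** On the plan's figures, zero lies 1.8 / 2.9 = 0.62 SD below the lower mean. A normal curve would put Φ(−0.62) = 27% of men below the bottom of the scale, so the scores must be skewed. I modelled them as beta-binomial on 0-10 with means 3.8 and 1.8 and SD 2.9 in both arms.

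- About 59% of the lower arm score zero. The medians are 3 and 0, a difference of 3 against a mean difference of 2. If only the lower arm's SD is reduced to 2.0, the medians are 3 and 1 and the difference is 2. The gap between the two measures therefore depends on the shape of the scores.
- The two tests reach different verdicts in about 15% of trials at 32 per arm and 10% at 43; across simulation runs the range is about 9 to 15%. With rounded normal scores truncated to 0-10, a milder shape, it is about 5% at 34 per arm and 3% at 43.
- Power at 32 per arm is about 76% for the t-test and 92% for the Wilcoxon. With the rounded, truncated normal at 34 per arm, both are 76%.
- With no true difference, choosing the test by a Shapiro-Wilk check or by a skewness rule gave type I error of 4.2 to 5.4% across the scenarios run.

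**The case against.** The strongest reply is that nothing here is invalid. After blocked randomisation with no named stratification factor, an unadjusted comparison is sound, and selecting a test by distribution leaves the error rate essentially nominal. That stands, and it limits the point to efficiency and clarity of the effect measure.

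Second, the predictive value of age and prior surgery is unknown. That stands too. The covariate usually most useful, pre-operative pain, is not clearly collected, since Table 1 does not time the day-of-surgery score. At R² of 0.02 the gain is under one percentage point. The case rests on the cost being close to nil, not on a promised benefit.

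Third, if scores pile up at zero, the Wilcoxon is the stronger test, by more than adjustment is likely to recover. This is a real trade-off. Fixing the mean difference is justified because the trial states its goal as two points on the mean.

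Fourth, the GEE already supplies a model-based comparison. It pools days 1 to 7, is additional to the day-7 test, and is also unadjusted, so it does not settle the day-7 measure.

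A reader might go further and infer that the t-test will seldom be used. The documents do not support this, because the answer depends on a rule they do not contain. With no difference between arms (means 3.8, SD 2.9), a 5% Shapiro-Wilk check sends about 94 to 99% of beta-binomial trials to the Wilcoxon; a rule of skewness above 1 sends 1 to 3%.

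A reader might also infer a raised false-positive rate. Inflation, to about 5.2 to 6.7%, appears only if the smaller of the two p-values is taken, and the plan does not say that this will be done.

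**Conclusion.** The point holds as a gap in specification and a missed gain in precision, not as an error of validity. The plan sizes for a mean difference, leaves the day-7 effect measure open between mean and median, and uses no baseline factor in any pain comparison.

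Adjustment gains about 0.8 to 8.4 percentage points of power at 32 per arm for R² of 0.02 to 0.20, and loses under 0.1 point at R² of zero. The R² values are assumptions. The power figures use ordinary model standard errors with a common SD of 2.9; robust errors could shift them slightly. The median gap and the test disagreement rest on an assumed score shape and are smaller for milder skew.

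**What to change.** In 12.2, before unblinding:

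- Name one primary effect measure: the difference in mean day-7 NRS-11 with its 95% CI. Estimate it from a linear model with arm, age (continuous) and prior scrotal or testicular surgery (yes/no), using robust standard errors such as HC3, whatever the score distribution.
- Put the same two covariates in the pain GEE.
- Report the Wilcoxon as a labelled sensitivity analysis that does not replace the primary result.
- State which day-7 score enters the model, or that the day's scores are averaged, since surveys are due every 12 hours on days 3 to 7 (11.1 and 12.1).

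The cost is wording, two degrees of freedom, and complete baseline records. Section 15 lists only surgical history in general, so the yes/no item must be defined and recorded before randomisation. The SAP should also say openly that a rank test may have more power if many men score zero, and that the mean was chosen to match the two-point goal. No extra participants are needed.

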#### **7.7 Dosing and Administration**

Each participant will receive the same dose of the drug.

Gabapentin will be administered as a single dose pre-operatively 600 mg and then 300mg three times a day for three post-operatively.

Placebo medication will be administered in the same fashion.

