## **12. Statistical Considerations**

### **12.1 Study Design/Endpoints**

The study will be a randomized double blind placebo controlled trial. We will randomize 86 study participants into two arms, with equal numbers in each arm.

Both the control arm and intervention arm will receive medication to be taken 2 hours before surgery as well as for three days three times a day after surgery. The team will be blinded to medication each study participant is receiving and will be recorded using a subject coded system.

Participants will receive reduced oxycodone prescriptions (quantity to be determined by clinical practice and prescribing surgeon) as needed, as well as celecoxib and acetaminophen to be taken as prescribed for the peri-operative period and up to 7 days post-operatively.

During the 7 subsequent post-op days participants in both the intervention and control arms will be asked to maintain a pain diary. The diary will be implemented online through the REDCap platform, which allows for secure online surveys. To ensure maximum compliance, subjects will be prompted by email, phone, or with a text message to their mobile phone. To ensure HIPAA compliance, text messages will only read as "A new survey is due." Participants will be informed of this prompting protocol beforehand. No PHI, or any details of medical therapy, will be revealed in the text message or in the surveys administered through REDCap (please see the survey attachment to review how each survey will appear). Texts will be sent from a study dedicated phone controlled by the study staff. The study phone will be encrypted and managed by ITS per WCM regulation. Subjects will complete surveys at the following intervals: every 8 hours post-operative day 1 and 2, Every 12 hours post-operative day 3 through 7.

Participants will be monitored for adverse events by the pre-operative nurses as well as the post-operative anesthesia care nurses who will be counselled on symptoms to examine for. Participants will have the opportunity to document any adverse events on their surveys.

Our primary endpoint will be to compare participant reported pain between participants receiving gabapentin and those receiving placebo in addition to standard of care. This will be assessed using the 11-point numerical pain rating scales (NRS-11) from post-operative day 1 to 7.

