## **12.6 Reporting and Exclusions**

### **12.6.1 Evaluation of Toxicity**

The frequency of subjects experiencing toxicities in each research study arm will be tabulated. Toxicities will be assessed and graded according to CTCAE v. 5.0 terminology. Exact 95% confidence intervals around the toxicity proportions will be calculated to assess the precision of the obtained estimates.

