### **13.4 Time Period and Frequency for Event Assessment and Follow Up**

The occurrence of an adverse event (AE) or serious adverse event (SAE) may come to the attention of study personnel during study visits and interviews of a study participant presenting for medical care, or upon review by a study monitor.

All AEs including local and systemic reactions not meeting the criteria for SAEs will be captured on the appropriate case report form (CRF). Information to be collected includes event description, time of onset, clinician's assessment of severity, relationship to study product (assessed only by those with the training and authority to make a diagnosis), and time of resolution/stabilization of the event. All AEs occurring while on study must be documented appropriately regardless of relationship. All AEs will be followed to adequate resolution.

Any medical condition that is present at the time that the participant is screened will be considered as baseline and not reported as an AE. However, if the study participant's condition deteriorates at any time during the study, it will be recorded as an AE.

Changes in the severity of an AE will be documented to allow an assessment of the duration of the event at each level of severity to be performed. AEs characterized as intermittent require documentation of onset and duration of each episode.

The primary investigator will record all reportable events with start dates occurring any time after informed consent is obtained until 7 (for non-serious AEs) or 30 days (for SAEs) after the last day of study participation. At each study visit, the investigator will inquire about the occurrence of AE/SAEs since the last visit. Events will be followed for outcome information until resolution or stabilization.

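### The between-arm adverse-event tests in section 12.2 start after surgery rather than at first dose, and no between-arm difference is planned for the expected drug effects

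*Combined protocol and SAP*

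**What the plan says.** Section 12.2 uses a chi-square or Fisher's exact test "to compare the proportion of adverse events experienced post-scrotal surgery between the two arms". It then adds: "Similar analyses will also be completed on the NRS-11 pain score, narcotic use, and reported adverse events on day-1 post-scrotal surgery". No other between-arm comparison of harm is planned.

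Dosing starts before that window. Section 7.7 reads: "Gabapentin will be administered as a single dose pre-operatively 600 mg and then 300mg three times a day". Sections 3.3 and 12.1 place the first dose 2 hours before surgery. Section 12.1 also says: "Participants will be monitored for adverse events by the pre-operative nurses as well as the post-operative anesthesia care nurses".

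Section 13.4 records events from informed consent, with time of onset, and requires: "All AEs occurring while on study must be documented appropriately regardless of relationship". Section 13.1.2 gives a five-level attribution scale, and section 15 lists Major and Minor events expected with the drug. Section 12.2 refers to neither.

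Section 12.6.1 is the other safety analysis: "The frequency of subjects experiencing toxicities in each research study arm will be tabulated". It continues: "Toxicities will be assessed and graded according to CTCAE v. 5.0 terminology", and then: "Exact 95% confidence intervals around the toxicity proportions will be calculated to assess the precision of the obtained estimates". It sets no post-surgery start and states no between-arm difference.

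**The concern.** Three features of the 12.2 test do not match the rest of the plan.

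- **Start.** Treatment begins with the pre-operative capsules, but the comparison begins after surgery. An episode of dizziness or somnolence that starts and resolves in the pre-operative area is a treatment-emergent event. It is observed and logged, yet it lies outside the test.
- **Unit.** A proportion of events could mean participants or events. A chi-square or Fisher test needs independent units, and one participant can have several events.
- **Target.** No event term, grade or attribution class is named. If every logged event counts, ordinary surgical events enter the same proportion as the sedation-type effects the protocol expects.

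At stake is how a non-significant result would be read. If it came from a test with little power for those effects, it could be taken as evidence that adding gabapentin does no harm.

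**Working it through.** **1. The plan's own figure.** The documents give no adverse-event rate and no power for safety, so the only figure to reproduce is the sample size. Inputs from 12.2: difference 2, SD 2.9, two-sided alpha 0.05, power 80%. The normal formula gives n = 2 × (1.960 + 0.842)² × 2.9² / 2² = 33.0, just above 33, so 34 per arm. The exact t calculation also gives 34. Then 34 × 1.25 = 42.5, rounded up to 43 per arm, 86 in total. This matches the plan. I use 43 per arm below.

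**2. What the window leaves out.** Set side by side:
- first dose 2 hours before surgery (3.3, 12.1);
- observation by pre-operative nurses (12.1) and recording from consent (13.4);
- comparison of events after surgery, and on day 1 (12.2).

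The excluded interval is about 2 hours plus the operation. With the 5 to 7 hour half-life in section 2.2, simple decay leaves 0.5^(2/5) = 76% to 0.5^(2/7) = 82% of the drug level 2 hours after the dose. Effects of the 600 mg dose therefore continue into the counted period. What is lost is confined to events that both begin and end before it.

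The share of events lost is unknown. As an illustration, take assumed rates of 10% v 30% (normal approximation, 43 per arm). If 10%, 25% or 50% of the 20-point excess fell wholly before the window, the gabapentin rate would be 28%, 25% or 20%, and power would fall from 64% to 57%, 45% or 25%.

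**3. What pooling would do.** Let d be the probability of a drug-type event and b the probability of an unrelated event, independent and equal in both arms. The probability of any event is 1 − (1 − b)(1 − d), so the difference between arms shrinks by the factor (1 − b). Power comes from full enumeration of the two binomials, 43 per arm, two-sided 0.05. All rates are assumed.

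| Background b | Any event, d = 10% v 35% | Chi-square power | Fisher power |
|---|---|---|---|
| 0% | 10.0% v 35.0% | 83% | 74% |
| 10% | 19.0% v 41.5% | 64% | 55% |
| 30% | 37.0% v 54.5% | 37% | 28% |
| 50% | 55.0% v 67.5% | 24% | 17% |
| 70% | 73.0% v 80.5% | 13% | 9% |

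For d = 10% v 25%, chi-square power is 47% with no background and 17%, 12% or 8% with a background of 30%, 50% or 70%.

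**4. Limits of a drug-event test.** With 34 analysed per arm, 10% v 35% has 73% power and 10% v 25% has 38%. At 43 per arm, 10% v 18% has 20%. Restricting the test to drug-type events removes the dilution but does not make the trial large enough to rule out modest harm.

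**5. Precision of an estimate.** At 10% v 35% the standard error of the risk difference is √(0.10 × 0.90/43 + 0.35 × 0.65/43) = 0.086. The 95% interval is 25 ± 17 points, about 8 to 42.

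**The case against.** The strongest reply is that safety reporting does not rest on the 12.2 test. Section 12.6.1 counts subjects by arm, in CTCAE terms with grades and exact intervals, and has no post-surgery limit. Dizziness and somnolence, including pre-operative onset, can be reported from it. That stands: the early events are missing from the comparison, not from the reporting. It does not close the gap, because an interval around each arm's proportion is not an interval for the difference. The general promise in 12.2 of intervals for parameters of interest does not say that such a difference is one of them.

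A reader might infer that everything following the 600 mg dose is lost, or use the share of milligrams taken before surgery as a measure of what the test misses. The documents support neither. The half-life carries that dose into the counted period, and milligrams swallowed measure neither exposure nor events.

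A reader might also infer that 12.2 commits to a single pooled proportion of events. It does not say so; it is silent on event type. The parallel wording on narcotic use, and the counting of subjects in 12.6.1, suggest that participants were meant. This is loose wording that permits a poor analysis, not proof that one is planned.

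Finally, the power figures depend on the assumed background. Section 15's list is mostly drug-type, pain is the primary outcome, and nausea is also collected as a survey symptom, so the background could be low. At 10% it still leaves 64% power.

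**Conclusion.** The point holds in a limited form. Both between-arm adverse-event comparisons in 12.2 start after surgery, so treatment-emergent events that begin and end earlier are collected but not compared. The number affected is unknown and may be small. Separately, no between-arm difference is planned for the expected drug effects, and the event definition in 12.2 leaves room for pooling with surgical events. If pooling were done, power for an assumed 10% v 35% would fall from 83% to between 64% and 13% as the background rises from 10% to 70%. That range rests wholly on assumed, independent rates and on 43 analysed per arm.

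A reader might infer that the trial will report false reassurance. The documents do not support that, since 12.6.1 lets the by-arm frequencies be seen. The primary pain comparison is unaffected. The change is worth making because it aligns 12.2 with the dosing, monitoring and recording that the protocol already specifies.

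**What to change.** - **Section 12.2.** Compare *the proportion of participants with at least one adverse event with onset at or after the first (pre-operative) capsule*. Count participants in the day-1 analysis as well.
- **Section 12.6.1.** Extend the by-arm table with between-arm risk differences and 95% confidence intervals for each event listed in section 15, covering all Major and Minor terms and including GI symptoms. A selected subset would be harder to defend.
- **Interpretation.** State that these differences are read as estimates, and that a non-significant result is not evidence of no harm.

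Cost: wording only. Events are already recorded from consent with time of onset (13.4), so no new data, visits or participants are needed and treatment is unchanged. The downside is a few more estimates to report, each imprecise at this sample size.
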